9.1.5. Post Data Collection Period to End of Study

The sponsor will ensure that subjects benefiting from treatment with either the IV or SC formulation of daratumumab will be able to continue receiving treatment after the end of the data collection period until the applicable formulation is commercially available or available from another source, or until the study is complete (Section 17.9.1). Attachment 13 describes study procedures to be followed for subjects who continue treatment with study drug after the end of the data collection period.

9.2. Efficacy Evaluations

9.2.1. Response Categories

Disease evaluations must be performed every 28 days (± 7 days), regardless of any changes to the dosing regimen, until disease progression. Disease evaluations will be performed by a central laboratory (unless otherwise specified). This study will use the IMWG consensus recommendations for multiple myeloma treatment response criteria (Durie 2006⁷; Kumar 2016¹¹; Rajkumar 2011²²) presented in Table 5. For quantitative immunoglobulin (QIg), M-protein, and immunofixation measurements in serum and 24 hour urine, the investigator will use results provided by the central laboratory. For subjects with light chain multiple myeloma, only serum FLC assay will be performed routinely. Otherwise, serum FLC assay test results will be analyzed by the central laboratory only for the assessment of sCR. For subjects with suspected daratumumab interference on serum M-protein quantitation by electrophoresis (SPEP) and immunofixation, a reflex assay will be performed (Attachment 10). Subjects with confirmed daratumumab interference who meet all other clinical criteria for CR or sCR will be considered CR/sCR.

Table 5: International Uniform Response Criteria Consensus Recommendations

Response	Response Criteria
Stringent complete Response (sCR)	
 CR as defined below, plus Normal FLC ratio, and Absence of clonal PCs by immunohistochemistry, immunofluorescence^a or 2- to 4-color flow cytometry
Complete response (CR)*	
 Negative immunofixation on the serum and urine, and Disappearance of any soft tissue plasmacytomas, and <5% PCs in bone marrow
Very good partial Response (VGPR)*	
 Serum and urine M-component detectable by immunofixation but not on electrophoresis, or $\geq 90\%$ reduction in serum M-protein plus urine M-protein <100 mg/24 hours
Partial response (PR)	
 $\geq 50\%$ reduction of serum M-protein and reduction in 24-hour urinary M-protein by $\geq 90\%$ or to <200 mg/24 hours If the serum and urine M-protein are not measurable, a decrease of $\geq 50\%$ in the difference between involved and uninvolved FLC levels is required in place of the M-protein criteria If serum and urine M-protein are not measurable, and serum free light assay is also not measurable, $\geq 50\%$ reduction in bone marrow PCs is required in place of M-protein, provided baseline bone marrow plasma cell percentage was $\geq 30\%$ In addition to the above criteria, if present at baseline, a $\geq 50\%$ reduction in the size of soft tissue plasmacytomas is also required.
Minimal response (MR)	
 $\geq 25\%$ but $\leq 49\%$ reduction of serum M-protein, and Reduction in 24-h urine M-protein by 50–89% In addition to the above criteria, if present at baseline, a 25% to 49% reduction in the size of soft tissue plasmacytomas also is required
Stable disease (SD)	
 Not meeting criteria for CR, VGPR, PR, MR, or PD
Progressive disease (PD) [†]	
 Increase of 25% from lowest response value in any one of the following: 
 Serum M-component (absolute increase must be ≥ 0.5 g/dL), Urine M-component (absolute increase must be ≥ 200 mg/24 hours), Only in subjects without measurable serum and urine M-protein levels: the difference between involved and uninvolved FLC levels (absolute increase must be >10 mg/dL) Only in subjects without measurable serum and urine M-protein levels and without measurable disease by FLC levels, bone marrow PC percentage (absolute percentage must be $\geq 10\%$) Bone marrow plasma cell percentage: the absolute percentage must be >10% Definite development of new bone lesions or soft tissue plasmacytomas or definite increase in the size of existing bone lesions or soft tissue plasmacytomas Development of hypercalcemia (corrected serum calcium >11.5 mg/dL) that can be attributed solely to the PC proliferative disorder

Table 5: International Uniform Response Criteria Consensus Recommendations

Response	Response Criteria
	
CR=complete response; FLC=free light chain; IMWG=International Myeloma Working Group; M-protein=monoclonal paraprotein; MR=minimal response; PC=plasma cell; PD=progressive disease; PR=partial response; sCR=stringent complete response; SD=stable disease; VGPR=very good partial response
 
All response categories (CR, sCR, VGPR, PR, and PD) require 2 consecutive assessments made at any time before the institution of any new therapy; CR, sCR, VGPR, PR, and SD categories also require no known evidence of progressive or new bone lesions if radiographic studies were performed. VGPR and CR categories require serum and urine studies regardless of whether disease at baseline was measurable on serum, urine, both, or neither.
 
Radiographic studies are not required to satisfy these response requirements. Bone marrow assessments need not be confirmed. For PD, serum M-component increases of more than or equal to 1 g/dL are sufficient to define relapse if starting M-component is ≥ 5 g/dL.
 
* Clarifications to IMWG criteria for coding CR and VGPR in subjects in whom the only measurable disease is by serum FLC levels: CR in such subjects indicates a normal FLC ratio of 0.26 to 1.65 in addition to CR criteria listed above. VGPR in such subjects requires a >90% decrease in the difference between involved and uninvolved FLC levels.
 
† Clarifications to IMWG criteria for coding PD: Bone marrow criteria for PD are to be used only in subjects without measurable disease by M protein and by FLC levels; “25% increase” refers to M protein, FLC, and bone marrow results, and does not refer to bone lesions, soft tissue plasmacytomas, or hypercalcemia and the “lowest response value” does not need to be a confirmed value.
 
^a Presence/absence of clonal cells is based upon the kappa/lambda ratio. An abnormal kappa/lambda ratio by immunohistochemistry or immunofluorescence requires a minimum of 100 plasma cells for analysis. An abnormal ratio reflecting presence of an abnormal clone is kappa/lambda of >4:1 or <1:2.
 
Clinical Relapse
 
Clinical relapse is defined using the definition of clinical relapse in IMWG criteria (Durie 2006⁷; Kumar 2016¹¹; Rajkumar 2011²²). In IMWG criteria, clinical relapse is defined as requiring one or more of the following direct indicators of increasing disease or end-organ dysfunction that are considered related to the underlying plasma cell proliferative disorder:
 
 1. Development of new soft tissue plasmacytomas or bone lesions on skeletal survey, magnetic resonance imaging, or other imaging 2. Definite increase in the size of existing plasmacytomas or bone lesions. A definite increase is defined as a 50% (and at least 1 cm) increase as measured serially by the sum of the products of the cross-diameters of the measurable lesion 3. Hypercalcemia (>11.5 mg/dL; >2.875mM/L) 4. Decrease in hemoglobin of more than 2 g/dL (1.25 mM) or to less than 10 g/dL 5. Rise in serum creatinine by more than or equal to 2 mg/dL (≥ 177 mM/L) 6. Hyperviscosity 
In some subjects, bone pain may be the initial symptom of relapse in the absence of any of the above features. However, bone pain without imaging confirmation is not adequate to meet these criteria in studies.


M-protein levels need to meet the definition of disease progression (see [Table 5](#)) for subjects to have disease progression. Disease evaluations will continue beyond relapse from CR until disease progression is confirmed.

Disease progression must be consistently documented across clinical study sites using the criteria in [Table 5](#). It is important that instances of disease progression be reported to the sponsor as soon as possible. Diagnosis and documentation of disease progression will be reported to the sponsor within 24 hours of suspected disease progression. The medical monitor will review the information to confirm that the IMWG criteria for disease progression have been met. If the medical monitor agrees that disease progression has occurred, then a confirmation will be returned to the investigator, and the subject will be withdrawn from study treatment. If the medical monitor considers that the IMWG criteria for disease progression have not been met, then the medical monitor will contact the investigator to discuss the subject.

For continuation of treatment, the IMWG response will be determined on an ongoing basis by the investigator. For data analysis and reporting, however, the sponsor will use a validated computer algorithm that has been shown to provide consistent review of the data necessary to determine disease progression and response according to IMWG criteria.

For subjects who discontinue study treatment before disease progression, disease evaluations should continue to be performed as described in the Time and Events Schedule, until confirmed disease progression, death, start of a new treatment for multiple myeloma, withdrawal of consent for study participation, or the end of the data collection period, whichever occurs first. Blood and urine for disease evaluations scheduled for treatment days should be collected before study treatment is administered.

Refer to [Attachment 13](#) details on efficacy evaluations after the end of the data collection period.

9.2.2. Myeloma Protein Measurements in Serum and Urine

Blood and 24-hour urine samples will be collected as specified in the Time and Events Schedule until the development of confirmed disease progression. Samples for M-protein measurements will be sent to and analyzed by a central laboratory. Only 1 serum and one 24-hour urine sample per time point are required by the central laboratory to perform the following tests:

- Serum QIGs: All subjects will be evaluated for IgG, IgA, IgM, IgE, and IgD at Screening. During the study, subjects with IgD or IgE disease will be evaluated for IgG, IgA, IgM, IgE, and IgD and subjects with IgG, IgA, or IgM disease will be evaluated for IgG, IgA, and IgM.
- Serum M-Protein quantification by electrophoresis (SPEP)
- Serum immunofixation at Screening and thereafter when a CR is suspected. If daratumumab interference is suspected based on SPEP and immunofixation (IFE) results, additional reflex IFE testing may be performed.
- Serum FLC assay
- 24-hour UPEP
- Urine immunofixation at Screening and thereafter when a CR is suspected

Disease progression based on 1 of the laboratory tests alone must be confirmed by at least 1 repeat investigation. Disease evaluations will continue beyond relapse from CR until disease progression is confirmed.

Subjects with a urine M-protein on UPEP ≥ 100 mg/24h at Screening will provide samples for UPEP assessment on the same schedule as SPEP throughout the study according to the Time & Events Schedule. Subjects can stop collecting samples for UPEP assessments after C1D1 only if 1) they have urine M-protein < 100 mg/24h at Screening, or 2) they have measurable urine M-protein ≥ 100 mg/24h at Screening but then urine M-protein < 100 mg/24h at 2 consecutive post-baseline measurements. A urine sample for UPEP assessment should be obtained to document VGPR, CR, and sCR and at suspected disease progression for all subjects with

measurable disease by SPEP or UPEP (non-FLC), regardless of UPEP collection exemptions as described above.

Serum and urine immunofixation test and serum FLC assay will be performed at Screening and thereafter when a CR is suspected (when serum or 24-hour urine M-protein electrophoresis [by SPEP or UPEP] are 0 or nonquantifiable). For subjects with suspected daratumumab interference on serum immunofixation, another reflex assay using the anti-idiotypic mAb will be used to confirm daratumumab migration on immunofixation. Subjects that meet all other IMWG criteria for CR, and whose positive immunofixation is confirmed to be daratumumab, will be considered complete responders. However, for subjects with light chain multiple myeloma, serum FLC assay will be performed routinely. Serum immunofixation assay samples will be split into 2 aliquots, with 1 reserved for potential follow-on testing if daratumumab interference with immunofixation is suspected. As daratumumab is a monoclonal IgG antibody, additional serum samples may be utilized to monitor for potential daratumumab interference with immunofixation.

Note: All attempts should be made to determine eligibility of the subject based on the central laboratory results of screening blood and urine M-protein measurements. In exceptional circumstances, the local laboratory results of blood and urine M-protein measurements may be used to determine eligibility, but only if the results are clearly (eg, 25% or more) above the thresholds for measurability. In such cases, central laboratory results are still required to be obtained in order to establish baseline values and confirm the results from the local laboratory.

9.2.3. Serum Calcium Corrected for Albumin

Blood samples for calculating serum calcium corrected for albumin will be collected as specified in the Time and Events Schedule and analyzed centrally until the development of confirmed disease progression. Development of hypercalcemia (corrected serum calcium >11.5 mg/dL or 2.8 mmol/L) can indicate disease progression or relapse if it is not attributable to any other cause (see disease response criteria in [Table 5](#)). Calcium binds to albumin and only the unbound (free) calcium is biologically active; therefore, the serum calcium level must be adjusted for abnormal albumin levels (“corrected serum calcium”). The formula for adjustment is presented in [Attachment 5](#).

When blood is analyzed at a local laboratory, measurement of free ionized calcium is an acceptable alternative to corrected serum calcium to determine hypercalcemia. Free ionized calcium levels greater than the ULN (local laboratory reference ranges) are considered to be hypercalcemic for this study.

9.2.4. β 2-microglobulin and Albumin

Blood samples for β 2-microglobulin and albumin are to be collected at Screening and will be analyzed by the central laboratory and used for the assessment of International Staging System staging at study entry. The central laboratory will also measure albumin at any time during the study that a serum calcium sample is taken.

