 - a. hemoglobin ≥ 7.5 g/dL (≥ 5 mmol/L) (without prior red blood cells [RBC] transfusion within 7 days before the laboratory test; recombinant human erythropoietin use is permitted);
 - b. absolute neutrophil count $\geq 1.0 \times 10^9$ /L (prior growth factor support is permitted);
 - c. platelet count $\geq 50 \times 10^9$ /L (transfusions are not permitted within 7 days of testing to achieve this minimum platelet count);
 - d. aspartate aminotransferase (AST) $\leq 2.5 \times$ upper limit of normal (ULN);
 - e. alanine aminotransferase (ALT) $\leq 2.5 \times$ ULN;
 - f. total bilirubin $\leq 2.0 \times$ ULN; except in subjects with congenital bilirubinemia, such as Gilbert syndrome (in which case direct bilirubin $\leq 2.0 \times$ ULN is required);
 - g. estimated creatinine clearance > 20 mL/min per 1.73m^2 (refer to [Attachment 4](#));
 - h. albumin-corrected serum calcium ≤ 14 mg/dL (≤ 3.5 mmol/L) or free ionized calcium ≤ 6.5 mg/dL (≤ 1.6 mmol/L) (refer to [Attachment 5](#)).
8. Women of childbearing potential must commit to either abstain continuously from heterosexual sexual intercourse or to use 2 methods of reliable birth control simultaneously. This includes one highly effective form of contraception (tubal ligation, intrauterine device, hormonal [birth control pills, injections, hormonal patches, vaginal rings or implants] or partner's vasectomy) and one additional effective contraceptive method (male latex or synthetic condom, diaphragm, or cervical cap). Contraception must begin 4 weeks prior to dosing. Reliable contraception is indicated even where there has been a history of infertility, unless due to hysterectomy.
9. Women of childbearing potential must have a negative urine or serum pregnancy test at screening within 14 days prior to randomization.
10. Each subject (or their legally acceptable representative) must sign an Informed Consent Form (ICF) indicating that he or she understands the purpose of and procedures required for

the study and are willing to participate in the study. Subjects must be willing and able to adhere to the prohibitions and restrictions specified in this protocol, as referenced in the ICF.

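### Two printed thresholds, hypercalcemia in Protocol 9.2.3 and haemoglobin in inclusion criterion 7a, give different cut-offs in conventional and SI units

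*Protocol*

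**What the plan says.** **Calcium.** Protocol 9.2.3 defines hypercalcemia as "corrected serum calcium >11.5 mg/dL or 2.8 mmol/L" and says that it "can indicate disease progression or relapse if it is not attributable to any other cause", referring the reader to Table 5. The progressive-disease row of Table 5 (Section 9.2.1) reads "Development of hypercalcemia (corrected serum calcium >11.5 mg/dL) that can be attributed solely to the PC proliferative disorder", with no SI value. The separate clinical-relapse list in Section 9.2.1 has "Hypercalcemia (>11.5 mg/dL; >2.875mM/L".

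**Haemoglobin.** Inclusion criterion 7a (Section 4.1) requires "hemoglobin ≥ 7.5 g/dL (≥ 5 mmol/L". The clinical-relapse list includes "Decrease in hemoglobin of more than 2 g/dL (1.25 mM".

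**How the values are used.** Section 9.2.1 requires progression to be documented by the Table 5 criteria, has the medical monitor confirm it, and assigns response and progression for analysis to a validated computer algorithm (SAP 5.1.2). Section 9.2.3 has corrected calcium analysed centrally. Section 9.7 has haematology run by local laboratories. Section 4 allows no eligibility waivers and has the sponsor review key eligibility criteria before randomization.

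**The concern.** A threshold printed in two units should be one threshold. In 9.2.3 a reader working in mmol/L meets a lower calcium cut-off than a reader working in mg/dL. Hypercalcemia is a separate item in the Table 5 definition of progression. Progression enters PFS (second in the SAP 5.1.1 testing order) and duration of response. It also enters the investigator's ongoing call on continuing treatment and the investigator-assessed sensitivity analyses.

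In criterion 7a the two values set two different entry limits. Because local laboratories report haemoglobin, the limit applied could differ between sites.

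**Working it through.** **Calcium: the protocol's conversion factor (mg/dL divided by mmol/L)**

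| Source | Pair | Ratio |
|---|---|---|
| Inclusion 7h, "albumin-corrected serum calcium ≤ 14 mg/dL (≤ 3.5 mmol/L" | 14 / 3.5 | 4.0 |
| Attachment 1, absolute limit | 11 / 2.75 | 4.0 |
| Attachment 1, excess over upper limit of normal | 1 / 0.25 | 4.0 |
| 9.2.1, clinical-relapse list | 11.5 / 2.875 | 4.0 |
| 9.2.3 | 11.5 / 2.8 | 4.107 |

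The two correction formulas in Attachment 5 agree with 4.0: 0.8 mg/dL per g/dL of albumin is 0.08 mg/dL per g/L, and 0.08 / 0.02 = 4.0. Section 9.2.3 is the only total-calcium pair that departs from this factor.

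- 11.5 mg/dL: 11.5 / 4.0 = 2.875 mmol/L.
- 2.8 mmol/L: 2.8 × 4.0 = 11.2 mg/dL.
- Gap: 11.5 − 11.2 = 0.3 mg/dL, or 2.875 − 2.8 = 0.075 mmol/L.
- Example: 11.3 mg/dL is 11.3 / 4.0 = 2.825 mmol/L. It exceeds 2.8 mmol/L and does not exceed 11.5 mg/dL.

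Rounding does not explain the figure. To one decimal 2.875 becomes 2.9; only truncation gives 2.8. By contrast, the free ionized calcium pair in 7h (6.5 mg/dL with 1.6 mmol/L) does fit rounding, since 6.5 / 4.0 = 1.625. Using the molar factor of 4.008 (a general constant, not a protocol figure) changes little: 11.5 mg/dL becomes 2.869 mmol/L, and 2.8 mmol/L becomes 11.22 mg/dL.

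**Haemoglobin: the protocol's conversion factor (g/dL divided by mmol/L)**

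- Clinical-relapse list: 2 / 1.25 = 1.6.
- Criterion 7a: 7.5 / 5 = 1.5.
- 7.5 g/dL: 7.5 / 1.6 = 4.69 mmol/L.
- 5 mmol/L: 5 × 1.6 = 8.0 g/dL.
- Example: 7.8 g/dL is 7.8 / 1.6 = 4.875 mmol/L. It is eligible in g/dL and ineligible in mmol/L.

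The 5 is consistent with rounding 4.69 to a whole number; to one decimal it would be 4.7. With the usual monomer factor of 0.6206 mmol/L per g/dL (again a general constant), 7.5 g/dL is 4.65 mmol/L and 5 mmol/L is about 8.06 g/dL.

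**Direction.** The SI value is easier to meet for hypercalcemia, so it would produce more progression calls. It is harder to meet for haemoglobin entry, so it would admit fewer subjects.

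**The case against.** The strongest reply is that 9.2.3 does not set the progression rule. It only says what hypercalcemia can indicate and sends the reader to Table 5, which governs and prints a single value in mg/dL. Further safeguards follow: central calcium analysis, attribution solely to the plasma cell disorder, at least one repeat when progression rests on a single laboratory test (9.2.2), confirmation by the medical monitor, and the algorithm for the main analysis. All of this stands, and it limits the consequence. It does not make the two halves of the sentence in 9.2.3 agree.

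A reader might infer that Sections 9.2.1 and 9.2.3 give two rival SI cut-offs for progression. The documents do not support that. The 2.875 figure belongs to the clinical-relapse list, and the text after that list says M-protein must meet the Table 5 definition for a subject to have progressed. The mismatch lies inside 9.2.3, and between its SI value and Table 5.

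A reader might also infer that PFS depends on the unit a site reports in. That is not shown. Calcium is measured centrally, and nothing available shows the algorithm using 2.8 mmol/L. Its specification (SAP Attachment 2) is not in the text available here, so its calcium cut-off and unit can be neither confirmed nor faulted.

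On haemoglobin, the reply is that the SI value is merely a coarse rounding, that it is the stricter of the two and so cannot admit anyone below 7.5 g/dL, and that the sponsor reviews key eligibility. That is fair as to safety and endpoints. It leaves open that subjects between the two limits were treated differently at different sites.

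**Conclusion.** The point holds as a unit error in two printed decision thresholds. For calcium, the affected values are above 11.2 and up to 11.5 mg/dL (above 2.8 and up to 2.875 mmol/L). For haemoglobin, they run from 7.5 to just under 8.0 g/dL (about 4.69 to just under 5 mmol/L).

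This rests on the protocol's own conversions and on reading the greater-than sign in 9.2.3 as applying to both numbers. The documents do not say how many subjects fall in either band.

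The practical effect is probably small. Neither the C_trough co-primary endpoint nor the sample size is touched. It would be tempting to read the calcium error as biasing the treatment comparison, but the documents show no mechanism by which either band would favour one arm: reporting unit is a property of the laboratory or site, and randomization is central. The arithmetic is certain; an effect on any analysed endpoint is not established.

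**What to change.** Reconcile the two unit values in 9.2.3 with each other and with Table 5 and the clinical-relapse list in 9.2.1. Reconcile the two haemoglobin values in criterion 7a. The sponsor must state which values were intended; this review does not choose between them. Confirm that the computer algorithm, the site guidance and the pre-randomization eligibility review each used one consistent pair, and record the answer. If enrolment is already complete, the haemoglobin correction serves mainly to describe accurately who was eligible.

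The cost is two printed figures and one check of unit handling.
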